6.5.3 Liver Enzyme Increase

Liver toxicities in rodents and monkeys were not observed in the GLP toxicology studies. To date, significant liver toxicity has not been reported in patients treated with selinexor. Patients should minimize their use of alcohol as this drug may deplete hepatic glutathione which could alter selinexor metabolism. Glutathione- (GSH-) replacing agents such as N-acetylcysteine or S-adenosylmethionine may be considered if selinexor induced liver dysfunction is suspected.

7 ADVERSE EVENT ASSESSMENT

The *Selinexor IB* is a reference source for selinexor and will be provided to the Investigators in the Investigator's File.

7.1 Adverse Events and Laboratory Abnormalities Reporting

7.1.1 Adverse Event

An adverse event (AE) is defined in the International Conference on Harmonisation (ICH) Guideline for Good Clinical Practice as "any untoward medical occurrence in a patient or clinical investigation subject administered a pharmaceutical product and that does not necessarily have a causal relationship with this treatment" (ICH E6: 1.2).

An adverse event can therefore be any unfavorable and unintended sign (including an abnormal laboratory finding, for example), symptom, or disease temporally associated with the use of a medicinal product, whether or not it is considered related to the medicinal product.

Pregnancy *per se* is not considered an AE. A medical occurrence observed in the mother or fetus/newborn would be an AE.

All AEs will be collected from the start of treatment, i.e., Cycle 1 Day 1, until 30 days (\pm 7 days) after the last dose of study medication.

Table 5: Classification of Adverse Events by Causality

Class	Description
Not related	The lack of a temporal relationship of the event to study treatment makes a causal relationship not reasonably possible, or by any other drugs, therapeutic interventions or underlying conditions that provide a sufficient explanation.
Possibly related	The temporal relationship of the event to study treatment makes a causal relationship reasonably possible, and the event is more likely explained by exposure to the study treatment than by any other drugs, therapeutic interventions or underlying conditions.
Related	The temporal relationship of the event to study treatment makes a definitive relationship, and the event is more likely explained by exposure to the study treatment than by any other drugs, therapeutic interventions or underlying conditions.

For the purpose of safety analyses, all AEs that are classified as related or possibly related will be considered treatment-related events.

The Investigator is responsible for ensuring that all adverse events observed by the Investigator or reported by patients are properly recorded in the patients' medical records and the electronic case report form.

The Investigator must assign the following attributes:

-
- Severity grade according to the NCI CTCAE criteria Version 4.03
 - Start date and stop date (or date of last assessment)
 - Outcome
 - Causality to study drug and chemotherapy (to be assessed as either related or not related)
 - Any action taken with the study drug

Pre-existing diseases, when worsening during study therapy, have to be considered as adverse events. They can lead to serious adverse events, if they meet the criteria described in Section 7.1.4.

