7.1.2 Adverse Drug Reaction

Adverse drug reactions (ADRs) include all untoward and unintended responses to a medicinal product related to any dose administered.

The phrase “responses to a medicinal product” means that a causal relationship between the medicinal product and the AE is at least a reasonable possibility, i.e. the relationship cannot be ruled out.

A serious ADR (SADR) is an ADR that meets the definition of serious (provided below).

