7.1.6 Suspected Unexpected Serious Adverse Reaction (SUSAR)

Per the definitions provided above, SUSARs are adverse events that have been determined by the investigator to be serious, suspected of being caused by selinexor (related or possibly related) and are unexpected according to the most current version of the investigator's brochure for selinexor.

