Appendix 4: Adverse Event Categories for Determining Relationship to Test Drug

(a) Related (must satisfy one of the following)

This category applies to those adverse events that are considered to be related to the test drug. An adverse event may be considered related if:

1. It follows a reasonable temporal sequence from administration of the drug
2. It cannot be reasonably explained by the known characteristics of the subject's clinical state, environmental or toxic factors or other modes of therapy administered to the subject
3. It disappears or decreases on cessation or reduction in dose. (There are important exceptions when an adverse event does not disappear upon discontinuation of the drug, yet drug-relatedness clearly exists: e.g. (1) bone marrow depression, (2) tardive dyskinesias.)
4. It follows a known pattern of response to the suspected drug
5. It reappears upon rechallenge

(b) Not related

This category is applicable to those adverse events which are judged to be clearly and incontrovertibly due only to extraneous causes (disease, environment, etc.) and do not meet the criteria for drug relationship listed under related.

Appendix 5: Definitions According to ICH Topic E2A Clinical Safety Data Management, Definitions and Standards for Expedited Reporting

An adverse event is any untoward medical occurrence in a patient or clinical investigation subject who has been administered a pharmaceutical product, and which does not necessarily have to have a causal relationship with this treatment.

Adverse reactions are defined as all untoward and unintended responses to an investigational medicinal product related to any dose administered. The phrase "responses to a medicinal products" means that a causal relationship between a medicinal product and an adverse event is at least a reasonable possibility, i.e., the relationship cannot be ruled out.

A serious adverse event or serious adverse reaction is any experience that suggests a significant hazard, contraindication, side effect or precaution. It is any adverse event that at any dose fulfills at least one of the following criteria:

- is fatal (results in death) (*NOTE: Death is an outcome, not an event*)
- is life-threatening (*NOTE: The term "life-threatening" refers to an event in which the patient was at immediate risk of death at the time of the event; it does not refer to an event which could hypothetically have caused a death had it been more severe*)

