- required in-patient hospitalisation or prolongation of existing hospitalisation
- results in persistent or significant disability/incapacity
- is a congenital anomaly/birth defect
- is medically significant or requires intervention to prevent one or other of the outcomes listed above

Medical and scientific judgement should be exercised in deciding whether expedited reporting to the sponsor is appropriate in other situations, such as important medical events that may not be immediately life-threatening or result in death or hospitalisation but may jeopardise the patient or may require intervention to prevent one of the outcomes listed in the definitions above. These situations should also usually be considered serious.

Examples of such events are intensive treatment in A&E or at home for allergic bronchospasm; blood dyscrasias or convulsions that do not result in hospitalisation, or development of drug dependency or drug abuse.

An unexpected adverse event, the nature or severity of which is not consistent with the applicable product information (e.g., Investigator's Brochure for an unapproved investigational medicinal product)

Causality is initially assessed by the Investigator. With respect to the obligation to report and document (regulatory authorities, ethics committees and other Investigators) serious adverse events, causality can be one of two possibilities:

- No (not related; equals not drug-related)
- Yes (remotely, possibly or probably drug-related)

All adverse events not assessed as definitively “not drug-related” by the Investigator will be considered as adverse drug reactions.

A suspected unexpected serious adverse reaction (SUSAR) is a serious adverse reaction whose nature or severity is not consistent with the applicable product information.

It is important that the severity of an adverse event is not confused with the seriousness of the event. For example, vomiting which persists for many hours may be severe, but is not necessarily a serious adverse event. On the other hand, stroke which results in only a limited degree of disability may be considered a mild stroke, but would be a serious adverse event.

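### Table 5 sets a higher bar for a possibly related adverse event than the protocol's own reaction definition, and the causality scales are not reconciled

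*Protocol*

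**What the plan says.** The protocol gives four accounts of causality.

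- **Section 7.1.1, Table 5** has three classes. *Possibly related* needs timing that allows a causal link "and the event is more likely explained by exposure to the study treatment than by any other drugs, therapeutic interventions or underlying conditions". The *related* class repeats that clause and differs only in the strength of the temporal link. *Not related* applies when the timing excludes causation, "or by any other drugs, therapeutic interventions or underlying conditions that provide a sufficient explanation". That row is not grammatical; I read it as two alternative conditions.
- **Section 7.1.2** defines an adverse drug reaction as one where a causal relationship is "at least a reasonable possibility, i.e. the relationship cannot be ruled out".
- **Appendix 4** has two classes. *Related* needs only one of five criteria, the first being a reasonable temporal sequence. *Not related* is kept for events "clearly and incontrovertibly due only to extraneous causes".
- **Appendix 5**, on the duty to report and document, counts even remotely related events as a yes. It treats every event not definitively unrelated as a reaction.

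The attribute list in Section 7.1.1 asks the investigator for a two-level answer directly after the three-level table. Appendix 16, Section 2.2 (Maintenance Phase) also uses two levels.

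The label is used in the pooling rule under Table 5, the SUSAR definition (7.1.6), follow-up of drug-related events (7.3), and the related-event summaries (Protocol 8.4.4.1, SAP 4.5.2). It also decides whether an event more than 30 days after last dose counts as treatment-emergent.

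**The concern.** On any usual scale, *possibly related* catches events where the drug is one plausible cause among several. Table 5 does not let it do that, because both upper classes demand that the drug be the better explanation. The class adds little to *related*, and the pooled treatment-related category is narrower than the protocol's own idea of a reaction.

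This matters because every patient receives selinexor. There is no untreated arm against which to check attribution, so the related-event tables rest on investigator judgement and on the definition given to investigators. Competing causes are to be expected: Table 4 tells sites to rule out other causes of fatigue and anorexia. At stake are the related-event and related-SAE tables, the classification of unexpected serious events as SUSARs, and whether late events enter the treatment-emergent set.

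**Working it through.** Neither document states a related-event count, rate or threshold, so there is no figure to reproduce. The check is logical.

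**Step 1: a test event.** Take an event with plausible timing, where the drug cannot be ruled out and the underlying cancer is an equally or more likely cause.

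| Rule | Result |
|---|---|
| Section 7.1.2 | Adverse drug reaction |
| Appendix 4 | Related: the temporal criterion is met, and the cause is not incontrovertibly extraneous |
| Appendix 5 | Yes |
| Table 5, *related* | Fails: drug is not the more likely explanation |
| Table 5, *possibly related* | Fails for the same reason |
| Table 5, *not related* | Met if the cancer is a sufficient explanation; otherwise not met |

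So the event is either not related or has no class in Table 5. In the second case the two-level attribute still forces an answer. As the event has failed both related classes, *not related* is the likely entry, but that is an inference.

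**Step 2: direction.** Any event in Table 5's upper two classes has timing that makes causation at least reasonably possible, so it meets Section 7.1.2. The test event shows that the converse fails. Table 5 therefore picks out a subset of Section 7.1.2 events.

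**Step 3: bound.** Let A be the number of events meeting Section 7.1.2, s the share of these with an equally or more likely other cause, and T the number recorded as related or possibly related under Table 5. Then

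(1 − s) × A ≤ T ≤ A.

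The documents give no value for s, so its range is 0 to 1: at s = 0 nothing is lost, and at s = 1 all could be. The tables count patients rather than events, and the number of patients lost cannot exceed the number of events lost.

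**Step 4: does anything later repair it?**
- Pooling *related* with *possibly related* does not recover an event excluded from both.
- Counting missing causality as related (Protocol 8.4.1, SAP 3.10) does not reach an event actively recorded as not related.
- Using the strongest relationship across repeated episodes (Protocol 8.4.4.1) helps only if at least one episode was judged related.

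**Step 5: what is untouched.** All-cause treatment-emergent and serious event incidence within 30 days of last dose does not use the causality label.

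**The case against.** The strongest reply is that Table 5 need not be what investigators use. The recorded attribute has two levels, and the two-level scale is in Appendix 4, where plausible timing alone is enough for *related*. A site following Appendix 4 would, if anything, over-attribute. This stands: the undercount arises only where Table 5 is applied, and the protocol does not say which scale governs.

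Three stronger readings are tempting, and the documents do not support them.

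- **Every displaced event becomes not related.** The text does not say so: one whose rival cause is likelier but not sufficient falls in a gap.
- **The drug's main toxicities are systematically under-attributed, and SUSARs are lost with them.** Table 4 lists fatigue, anorexia and nausea among common selinexor-related toxicities, which steers sites towards attribution. These effects are also expected, so they cannot illustrate lost SUSARs. Section 7.2.1 requires all serious events to be reported within 24 hours, so Table 5 hides none from the sponsor's side, and Appendix 5 is inclusive. A route remains because Section 7.1.6 ties SUSAR status to the investigator's label.
- **The affected events are those with a probability of relation between zero and one half.** No such figure appears. With several candidate causes, being likelier than each other cause need not mean exceeding one half, and Section 7.1.2 asks for a reasonable possibility, not merely more than zero.

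It is also true that the related-event tables are descriptive, with no hypothesis test, and that the primary endpoint, disease control rate, does not depend on them.

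**Conclusion.** The contradiction holds on the text. Table 5 conflicts with Section 7.1.2, Appendix 4 and Appendix 5 on the threshold, and with the Section 7.1.1 attribute list and the Maintenance Phase on the number of levels. Compared with the Section 7.1.2 definition, applying Table 5 can only lower related-event and related-SAE counts. It may also lower SUSAR classification of unexpected serious events.

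This is a direction, not an amount. It rests on two assumptions: that at least some investigators worked from Table 5, and that some events had an equally or more likely other cause. It is a drafting inconsistency that should be corrected; it does not show that drug reactions have in fact been missed.

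**What to change.** 1. In Table 5, remove the more-likely condition from *possibly related*, so that it matches Section 7.1.2: at least a reasonable possibility that cannot be ruled out.
2. Limit *not related* to events where a relationship can be ruled out.
3. Use one scale in Table 5, the Section 7.1.1 attribute list, Appendices 4 and 5, and the Maintenance Phase. Rewording Table 5 and the attribute list alone would leave the appendices and the Maintenance Phase out of line.
4. State which scale feeds SUSAR reporting and the related-event tables of SAP 4.5.2.
5. For data already collected, state in the study report which definition was used. Section 1.4 puts 3 patients on treatment as of July 2016, so new wording will touch few new events and will not reclassify recorded ones.

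The cost is protocol wording, a note to sites and a statement in the report. The downside is that somewhat more events will be classed as related and reported.

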7.1.2 Adverse Drug Reaction

Adverse drug reactions (ADRs) include all untoward and unintended responses to a medicinal product related to any dose administered.

The phrase “responses to a medicinal product” means that a causal relationship between the medicinal product and the AE is at least a reasonable possibility, i.e. the relationship cannot be ruled out.

A serious ADR (SADR) is an ADR that meets the definition of serious (provided below).

7.1.3 Laboratory Test Abnormalities

Laboratory test results will be recorded on the laboratory results pages of the eCRF. In the event of unexplained abnormal laboratory test values, the tests should be repeated and followed up until they have returned to the normal range and/or an adequate explanation of the abnormality is found.

Laboratory test value abnormalities as such should not be reported on the AE page of the eCRF as adverse events unless they are treatment-emergent and they satisfy one or more of the following conditions for clinical significance:

1. Accompanied by clinical symptoms
2. Leading to a change in study medication (e.g., dose modification, interruption or permanent discontinuation)
3. Requiring a change in concomitant therapy (e.g., addition of, interruption of, discontinuation of, or any other change in a concomitant medication, therapy or treatment)

Please note: Any laboratory result abnormality fulfilling the criteria for a serious adverse event (SAE) should be reported as such, in addition to being recorded as an adverse event in the eCRF.

7.1.4 Serious Adverse Event

SAEs will be collected from the time of Informed Consent through 30 days (\pm 7 days) after the last dose of study medication.

A serious adverse event (SAE) is defined as an adverse event that meets one or more of the following:

- is fatal
- is life threatening (places the subject at immediate risk of death)
- requires in-patient hospitalization or prolongation of existing hospitalization
- results in persistent or significant disability/incapacity
- is a congenital anomaly/birth defect
- other important medical events

A hospitalization meeting the regulatory definition for “serious” is any inpatient hospital admission that includes a minimum of an overnight stay in a healthcare facility. Any adverse event that does not meet one of the definitions of serious (e.g. visit to A&E, outpatient surgery, or requires urgent investigation) may be considered by the Investigator to meet the “other significant medical hazard” criterion for classification as a serious adverse event. Examples include allergic bronchospasm, convulsions, and blood dyscrasias.

Important medical events are defined as those occurrences that may not be immediately life threatening or result in death, hospitalization, or disability, but may jeopardize the subject or require medical or surgical intervention to prevent one of the other outcomes listed above. Medical judgment should be exercised in deciding whether such an AE should be considered serious.

In addition, all cases of cerebellar toxicities of Grade 3 or higher must be captured as an SAE and reported to the regulatory authorities, IRBs, ECs, and Investigators in an expedited Safety Report within 7 days of awareness of the event.

7.1.5 Events NOT to be reported as SAEs

For this study, the following are **not** classified as SAEs:

- Progression or deterioration of the malignancy under study (including new metastatic lesions) or death due to progression.
- Hospitalization for the performance of protocol-required procedures or administration of study treatment. However, hospitalization or a prolonged hospitalization for a complication of therapy administration will be reported as an SAE.
- Hospitalization or procedures planned prior to study start. A pre-planned procedure must be documented in the source documents. However, hospitalization or prolonged hospitalization for a complication remains to be reported as an SAE.
- An elective hospitalization for a pre-existing condition not related to the studied indication.
- Hospital admission that is not associated with an adverse event (e.g., social hospitalization for purpose of respite care).

-
- Routine treatment or monitoring of the studied indication not associated with any deterioration in condition.
 - The administration of blood or platelet transfusion as routine treatment of studied indication. However, hospitalization or prolonged hospitalization for a complication of such transfusions remains to be reported as an SAE.
 - Emergency outpatient treatment or observation that does not result in admission, unless fulfilling other seriousness criteria above.

7.1.6 Suspected Unexpected Serious Adverse Reaction (SUSAR)

Per the definitions provided above, SUSARs are adverse events that have been determined by the investigator to be serious, suspected of being caused by selinexor (related or possibly related) and are unexpected according to the most current version of the investigator's brochure for selinexor.

7.2 Reporting of SAEs

7.2.1 Primary Treatment Phase

Any clinical adverse event or abnormal laboratory test value that is serious occurring during the course of the study from the date of signing the informed consent, irrespective of the treatment received by the patient, must be reported to GSO within 24 hours following knowledge of the SAE.

The following detailed information must be recorded for each serious adverse event in the SAE report form:

- The severity grade as assessed by the investigator according to the definitions in NCI-CTCAE Version 4.03
- The date of becoming serious and the date of becoming known (if different)
- The reason for seriousness
- The outcome of the SAE at the time of the report
- Information on administration of the study drug and chemotherapy and any action taken
- Information on any procedures necessary to treat the SAE, concomitant medications, relevant lab tests and relevant medical history

The completed SAE form must be sent to:

GSO

[contact]

Email: [contact]

Karyopharm Therapeutics will ensure the notification of the appropriate ethics committees, competent authorities and participating investigators of all SUSAR events occurring at the sites in accordance with local legal requirements, statutes and the European Clinical Trial Directive.

7.2.2 Maintenance Phase

See Section 18 (Appendix 16) for reporting of SAEs during the Maintenance Phase of the study (Version ≥3.2).

7.3 AE and SAE Follow-up

All AEs will be followed in accordance with good medical practice until they are resolved, stabilized or judged no longer clinically significant or, if a chronic condition, until fully characterized. Any AEs that are considered drug-related (possibly related or related) must be followed until resolution or until stabilization.

